In our previous study, "Incidence of Surgical Site Infections in Second Intention Healing After Dermatologic Surgery," Schimmel et al. compared a retrospective study of 5,679 patients investigating the rate of surgical site infection and associated pathogenic organisms of second intention wounds compared with sutured wounds after skin cancer extirpation. The infection rate for sutured and second intention wounds was 3.2% and 6.8%, respectively. Second intention wounds were associated with a significantly higher risk of infection compared with sutured wounds (odds ratio = 2.22, 95% confidence interval 1.63-2.99). The lower extremity (LE) had the highest overall infection rate (10.5%). *Staphylococcus aureus* was the most common organism cultured in both second intention (35%) and sutured wounds (81%). *Pseudomonas* was the second most common organism cultured in second intention wounds.

"Risk Factors for Surgical Site Infections in Dermatological Surgery" by Liu et al was an observational cohort study of 1,977 procedures in 1,407 patients investigating the parameters that lead to increased

risk of surgical site infections. Infection rates were increased in surgeries performed on the ear, larger wounds and defects closed with flaps or healed by second intention. Second intention was associated with a significantly higher risk of surgical site infection (OR 3.01, 95%CI 1.11–8.13). The surgical site infection rate of wounds healing by second intention was 6.1%. This number was higher than the accepted range in previous studies (0.7–4.2).

“Prospective study of wound infections in dermatologic surgery in the absence of prophylactic antibiotics,” by Dixon et al was a 3-year prospective study investigating the incidence of infection after surgical treatment of predominantly nonmelanoma skin cancer. No patients in the study received prophylactic antibiotics. Analysis of regions of the body demonstrated that surgery below the knee (n=448) had an infection incidence of 6.92% (31/448) (p<.0001). A sub-analysis demonstrated that all regions below the knee were at high infection risk. No other body site demonstrated an infection incidence beyond 5% of statistical significance.

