“Observations Regarding Infection Risk in Lower-Extremity Wound Healing by Second Intention,” by Molina et al, was a retrospective study of 555 patients treated with MMS on the lower extremities with wounds left for second intention healing was conducted investigating the rate of infection and pathogenic organisms. Of 555 patients, 24 patients (4.3%) returned to clinic with culture-positive wound infections within 90 days of surgery. The majority (n= 15, 63%) of infections were caused by *Staphylococcus aureus*.

“Oral Antibiotics Versus Topical Decolonization to Prevent Surgical Site Infection After Mohs Micrographic Surgery—a Randomized, Controlled Trial,” by Cherian et al was a randomized, controlled trial with 693 patients. Nasal carriers of *S. aureus* were randomized to receive topical decolonization with intranasal mupirocin twice daily plus 4% chlorhexidine gluconate body wash daily for 5 consecutive days before surgery or pre- and postoperative doses of oral cephalexin. Nine percent of patients receiving oral antibiotic prophylaxis and none of the patients receiving topical decolonization developed early SSI (p = .003).

“Randomized Controlled Trial of Preoperative Topical Decolonization to Reduce Surgical Site Infection for *Staphylococcus aureus* Nasal Swab-Negative Mohs Micrographic Surgery Patients,” by Smith et al was a randomized controlled trial of *S. aureus* nasal swab-negative patients. Five days before Mohs surgery topical decolonization with nasal mupirocin and chlorhexidine body wash was started. The control group had no intervention. Results demonstrated the infection rate in the intervention group was 2% and that of the control group was 4%.

A.2. Study Design

This study is a prospective, randomized trial. Patients will be randomly placed into one of two arms. The experimental group will receive decolonization with mupirocin 2% ointment to the nares and chlorhexidine washes to the skin folds and lower extremities. The control group will not receive any pre-operative decolonization. This is not a pilot study.

A.3. Intervention

Patients in our experimental group will apply mupirocin 2% ointment to each nostril twice daily five days prior to surgery. Chlorhexidine will be applied to the skin folds and lower extremities during the five

consecutive showers prior to surgery. Patients will be instructed to let the chlorhexidine sit for one minute prior to rinsing.

A.4. Allocation to Interventional Group

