Patients will be randomized to either the control (standard of care) group or the experimental (decolonization) group. A log will be kept allowing for randomization of patients into control arms. The log will alternate between study and control group. The patient will be entered into the log in the order that their telehealth was completed, which will determine their study group.

A.5. Sample Size Calculation

Our previous study determined a surgical site infection rate of ~10% in lower extremity surgical wounds healing by second intention. Given our assumption that the intervention would reduce the incidence to 5%, the minimal sample size necessary to detect a 5% absolute difference between the intervention and control group would be 424 per group for a total of 848 subjects. We plan to enroll subjects at 10 study centers in order to be able to reach the sample size required for adequate power.

A.6. Data Analysis Plan

Fisher's exact test will be used to compare categorical variables.

B. Subject Population

B.1. Description of Subject Population

This study will target any patients undergoing Mohs micrographic surgery or surgical excision on the lower extremities that will heal by second intention as determined by the surgeon performing the procedure.

B.2. Inclusion Criteria

- Individuals undergoing surgical treatment for skin cancer on the lower extremities.
- Postoperative wounds healing by second intention
- Must be at least 18 years old.

B.3. Exclusion Criteria

- Any individual taking antibiotics during the peri-operative period or post-operative period (for a reason other than surgical site infection)
- Patients with known intolerance or hypersensitivity to mupirocin or chlorhexidine.
- Patients that are currently pregnant or attempting to become pregnant.
- Patients with a history of *Staphylococcus aureus* infections.
- Patients with a history of heart valve or joint replacement requiring pre-operative antibiotics.

B.4. Eligibility Screening

All patients referred to our clinic for Mohs micrographic surgery or surgical excision will be screened for inclusion in this study. The scheduling staff will alert study physicians of any patient who is being scheduled for surgery on the lower extremity. Once flagged, a study physician will review the location and deem if patient an appropriate candidate for the study.

B.5. Recruitment

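### Is the ~10% control rate behind the sample size unsupported by the protocol's own account of the previous study?

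*Protocol*

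**What the plan says.** Section A.5 takes its control rate from the group's earlier work: "Our previous study determined a surgical site infection rate of ~10% in lower extremity surgical wounds healing by second intention". It continues "Given our assumption that the intervention would reduce the incidence to 5" per cent, and arrives at 424 per group, 848 in total. It closes with "We plan to enroll subjects at 10 study centers in order to be able to reach the sample size required for adequate power". Alpha, sidedness and a numerical power are not given.

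Background and Significance summarises the earlier study, a retrospective comparison of second-intention and sutured wounds in 5,679 patients:

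- By closure type: "The infection rate for sutured and second intention wounds was 3.2% and 6.8%, respectively".
- By site: "The lower extremity (LE) had the highest overall infection rate (10.5" per cent).
- The contrast: "Second intention wounds were associated with a significantly higher risk of infection compared with sutured wounds (odds ratio = 2.22".

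Two other cited studies bear on the leg. In one, "surgery below the knee (n=448) had an infection incidence of 6.92% (31/448"). In the other, a retrospective series of Mohs wounds on the lower extremity left to second intention, "Of 555 patients, 24 patients (4.3%) returned to clinic with culture-positive wound infections within 90 days of surgery".

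**The concern.** A.5 names a specific subgroup, lower-extremity wounds healing by second intention, and credits the previous study with a rate for it. The Background gives that study's rate by closure type and its rate by site, but never for the two together. The ~10% therefore looks as if the overall leg rate of 10.5% had been carried into A.5 under a narrower label.

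The one cited series whose population matches by site and closure reports less than half that rate, and A.5 does not say why it was passed over. Only the 5% intervention rate is called an assumption; the control rate is presented as a finding.

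The possible cost is a trial with too few events. If the true control rate were near 4% to 7%, 848 patients would give well under 80% power for a halving of risk. At 4.3%, the 5-point absolute reduction named in A.5 could not occur at all.

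**Working it through.** **Inputs.** From A.5: control 10%, intervention 5%, 424 per group. From the Background: 10.5% (leg, overall), 6.8% and 3.2% (second intention and sutured, all sites), odds ratio 2.22, 31/448 and 24/555. Assumed, because not stated: two-sided alpha 0.05, 80% target power, no dropout.

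**1. Reproduce 424.** Arcsine formula: n = 2[(z₀.₉₇₅ + z₀.₈₀)/h]², with h = 2 arcsin√0.10 − 2 arcsin√0.05 = 0.1925. This gives 2 × (2.8016/0.1925)² ≈ 423.7, so 424. The pooled-variance formula gives 435 and the unpooled one 432. The arithmetic is sound for its inputs.

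**2. Dependence on the control rate.** Exact power of the two-sided Fisher test (the test named in A.6), 424 per group, risk halved:

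| Control rate | What the figure is | Power |
|---|---|---|
| 4.3% | leg, second intention, returning culture-positive patients | 36% |
| 6.8% | second intention, all sites | 56% |
| 6.92% | below knee, not described as second intention only | 57% |
| 10% | A.5 | 76% |
| 10.5% | leg, overall | 78% |
| 12% | upward scenario (step 4) | 84% |

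The 76% at exactly 10% is a separate matter. It comes from analysing by Fisher's test a size that matches the arcsine formula (the uncorrected z-test gives 79%), and says nothing about the source of the rate.

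**3. Precision of the lower figures.** Exact 95% intervals: 24/555 = 4.3% (2.8% to 6.4%); 31/448 = 6.92% (4.7% to 9.7%). Both exclude 10%, but only for the populations and definitions those studies used.

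**4. What the previous study implies for the subgroup.** Suppose 10.5% pools both closure types and the odds ratio of 2.22 holds on the leg. Let s be the second-intention share of leg wounds, p the second-intention rate and q the sutured rate. Solve s·p + (1 − s)·q = 0.105 with [p/(1 − p)]/[q/(1 − q)] = 2.22. The protocol does not give s, so a range is shown:

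| s (assumed) | p | q | Power, p against p/2 |
|---|---|---|---|
| 75% | 12.1% | 5.8% | 85% |
| 50% | 14.1% | 6.9% | 91% |
| 25% | 16.9% | 8.4% | 95% |

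On this reading ~10% is cautious. If instead the 10.5% already describes mainly second-intention wounds, ~10% is simply that figure rounded. Neither reading makes A.5 too optimistic.

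**5. Comparability of the 4.3% series.** It is retrospective, limited to Mohs surgery, and counts only patients who came back and had a positive culture. The trial also takes excisions, asks every patient for photographs at weeks 2 and 4, and telephones at one month those without a follow-up visit (sections C.1 and C.2). These features tend to find more infections. The shorter follow-up (one month against 90 days) and the exclusion of patients with earlier *Staphylococcus aureus* infection (B.3) work the other way. The net direction cannot be settled from the protocol.

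**The case for a change.** The strongest case for a change is that a protocol should show where its key planning figure comes from, and this one does not. The sentence in A.5 goes beyond what the Background reports. The only cited series matching on site and closure has a confidence interval that excludes 10%. Power runs from 36% to 95% across rates that the protocol's own figures allow. One paragraph giving the count, a reason for preferring it to 4.3% and power at several rates would cost nothing in enrolment or conduct.

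Much of this stands. The subgroup rate is not printed in the Background, power does depend heavily on it, and A.5 would read better with the numerator and denominator.

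Three parts do not stand. First, a short summary that omits a figure does not show the figure to be wrong; the earlier study is the sponsor's own and compared closure types, so it may well hold the count. Second, the risk is not all downward: a table stopping at 10% would mislead as much as no table, and the 6.92% comparator has the same population gap that is held against A.5. Third, a null result will be judged from the observed event counts and the confidence interval for the difference, not from the planning rate, so readers will not be left unable to tell whether it is informative.

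**Conclusion.** No change to the plan is needed. The protocol attributes ~10% to its previous study without displaying the subgroup count, and that is a gap in presentation. It does not contradict the 10.5% overall leg rate, and the study's own odds ratio gives reason to expect a second-intention rate at or above 10% if that figure pools closure types.

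The consequence of a wrong rate would be real: 36% power at 4.3% against 76% at 10%, assuming two-sided alpha 0.05, halved risk, Fisher's test and 424 analysed per group. But the protocol supports departures in both directions and does not establish either. A.5 commits to no numerical power that the design then misses, and a sensitivity table with alpha and dropout is often left to the SAP, which is not at hand.

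Showing the source count, or saying that ~10% is the overall leg rate, would be a courtesy to the reader. It would leave the 848 patients, the conduct and the analysis as they are.

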It is not standard of care for patients undergoing Mohs micrographic surgery or excision on the lower extremities to decolonize with mupirocin 2% ointment and chlorhexidine. Although not standard of care, is commonly utilized by dermatologic surgeons for patients with a history of *Staphylococcus aureus* infections.

It is not standard of care for patients to complete a demographic surgery prior to their procedure.

C.7. Subject Withdrawal

Subjects can withdraw from the study at any time with no penalty by contacting the study team. Data that has already been collected will be retained, but not further data will be collected for research purposes.

If any patient experiences side effects to mupirocin ointment or chlorhexidine, such as burning, itching, or dryness at the application site, they will be instructed to alert the study staff. A physician from the study staff will then have a telephone consult with the patient about the side effects they are experiencing, and based on the physician evaluation, will either be asked to discontinue the medication and be removed from the study, or be counseled that it is safe to resume the study. Any patient that experiences side effects will be counseled that they may withdraw from the study at any time.

D. Additional Human Subject Considerations

D.1. Vulnerable Populations

There are no vulnerable populations involved in this study.

D.2. Economic Impact on Subjects

The only cost patients may have is the cost for the chlorhexidine and mupirocin ointment, depending on their insurance coverage.

D.3. Compensation

Patients will not be compensated for participating in this research study.

D.4. Treatment for Research-Related Injuries

The physicians that perform the procedures will provide treatment for any research-related injuries, such as infection treatment.

D.5. Sharing Study Results

If a wound culture is obtained from a patient, the results from the culture will be shared with them.

D.6. Risks

The patients involved in this study may encounter the following risks:

1. Patients have the possibility of developing side effects to the chlorhexidine and mupirocin treatment, such as burning, stinging, or dryness in the treatment area.
2. Patients may feel uncomfortable answering questions on the demographic questionnaire.
3. There is a risk of confidentiality if medical information or identity are obtained by someone other than the investigators, but precautions will be taken to prevent this from happening.

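### Section A.5 plans to reach 424 per group, a zero-loss minimum, so if 848 are enrolled any loss after allocation leaves fewer observed outcomes than the stated requirement

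*Protocol*

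**What the plan says.** Protocol A.5 starts from a control rate: "Our previous study determined a surgical site infection rate of ~10% in lower extremity surgical wounds healing by second intention". It assumes that decolonization brings this down to 5%. From these two rates it concludes that "the minimal sample size necessary to detect a 5% absolute difference between the intervention and control group would be 424 per group", and doubles that number: "424 per group for a total of 848 subjects". The next sentence concerns recruitment: "We plan to enroll subjects at 10 study centers in order to be able to reach the sample size required for adequate power". A.5 gives no alpha, sidedness or numerical power, no expected loss, and no enrolment figure apart from 848.

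A.6 names the test: "Fisher's exact test will be used to compare categorical variables".

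Other sections describe how an allocated patient can end without an outcome, or outside the study:

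- **C.7** allows withdrawal at any time, after which "Data that has already been collected will be retained, but not further data will be collected for research purposes". It also lets a physician remove a patient who has side effects from mupirocin or chlorhexidine. Only the experimental arm receives these.
- **B.3** excludes patients who take antibiotics post-operatively for a reason other than surgical site infection. This can become known only after allocation.
- **C.1 and C.2** obtain the outcome from photos that patients upload at weeks 2 and 4, from symptoms that patients report, and from a telephone call at one month.

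**The concern.** A number described as minimal has no margin by definition. Here the same number is what the ten centers are meant to reach. A calculation of this kind counts patients who contribute an outcome, whereas A.5 ties the number to patients enrolled. The two agree only if nobody is lost, and the protocol has rules for patients who are.

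The stake is how the result will be read. A.5 links 848 to "the sample size required for adequate power". If the trial enrolls 848, loses some outcomes and finds no significant difference, a reader will take A.5 as assurance that a halving of the infection rate would probably have been detected. The real chance of detecting it would be lower than that sentence implies, and the protocol offers no figure by which to judge how much lower.

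**Working it through.** **Inputs from the protocol.** Control rate 10%, experimental rate 5%, 424 per group, 848 in total (A.5); two equal arms (alternating log, A.4); Fisher's exact test (A.6).

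**Assumptions.** Two-sided alpha of 5% and 80% power. The protocol states neither, but together they reproduce its figure. The loss rates are also assumed, because the documents give none.

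**Step 1: reproduce 424.** The arcsine formula is n = 2(z₁ + z₂)² / h², where h = 2·arcsin√0.10 − 2·arcsin√0.05.

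- h = 0.6435 − 0.4510 = 0.1925 (unrounded 0.19247)
- z₁ + z₂ = 1.960 + 0.842 = 2.802 (unrounded 2.80159)
- n = 2 × 2.80159² / 0.19247² = 423.7, rounded up to 424

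Other common formulas with the same assumptions give 432 (unpooled), 435 (pooled) and 474 (continuity-corrected). The arcsine formula is the one that returns 424, and it does so with zero loss. The total adds nothing: 2 × 424 = 848.

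**Step 2: observed outcomes if 848 are enrolled.** Observed per group = 424 × (1 − loss).

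- 5% loss: 424 × 0.95 = 402.8, about 403
- 10% loss: 424 × 0.90 = 381.6, about 382

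**Step 3: power at those sizes, 10% against 5%.** Each value sums the binomial probabilities of all pairs of infection counts that the test rejects at two-sided 5%.

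| Loss (assumed) | Observed per group | Exact power, chi-square | Exact power, Fisher |
|---|---|---|---|
| none | 424 | 80.1% | 75.8% |
| 5% | 403 | 77.9% | 74.1% |
| 10% | 382 | 75.5% | 71.4% |

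**Step 4: separate the two effects.** Each column read downwards shows attrition alone. For chi-square it costs 80.1 − 77.9 = 2.2 points at 5% loss and 80.1 − 75.5 = 4.6 points at 10%. For Fisher it costs 75.8 − 74.1 = 1.7 and 75.8 − 71.4 = 4.4 points. The top row read across shows a difference of 80.1 − 75.8 = 4.3 points that is present with no loss. That difference arises because the arcsine formula does not describe Fisher's exact test, and it is not part of the attrition effect.

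**Step 5: scale, for reference.** Keeping 424 observed per group would take 424 / 0.95 = 446.3, so 447 per group, at 5% loss, and 424 / 0.90 = 471.1, so 472 per group, at 10%.

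**The case against.** **The arithmetic in A.5 is right.** Correct. 424 is reproduced and 848 is twice 424. The point is what the number is taken to count.

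**848 could mean patients with an outcome.** A.5 sets no cap and does not say that enrolment stops at 848, and a minimal size can be read as the number needed for analysis. The wording allows this, although A.5 ties the figure to enrolment. It does not remove the point: on that reading A.5 gives no enrolment figure at all, and the same clarification is needed.

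**Follow-up is stronger than a list of weak points suggests.** This stands. A reader might infer that each unanswered photo request is a lost outcome, but the documents do not support that. Symptoms can bring a patient in at any time, there is a call at one month, and D.6.1 item 4 provides a telephone line and says that study staff will contact every enrolled patient one month after the procedure. The outcome is missing only if all routes fail. Follow-up lasts one month, and data collected before a withdrawal are kept.

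**The size of any shortfall comes from outside the documents.** This also stands. A reader might infer that the trial will certainly be underpowered, or that losses of 15% or 20% should be expected. With no loss rate in the protocol, neither can be claimed. Nor does the protocol state a numerical power from which to measure a fall; the 80% is inferred because it reproduces 424.

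**The Fisher figures make attrition look worse.** They would if the fall from 80% to 71% were all put down to loss. About half of it is the separate mismatch between formula and test.

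**Conclusion.** The point holds in a limited form. A.5 sets a minimum with no margin, gives it as the only size that enrolment is to reach, and allows nothing for losses that C.7, B.3 and the follow-up procedures foresee. If 848 are enrolled, any loss after allocation puts the observed number below 424 per group, whichever test is used.

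The effect is moderate: about 2 points of power at 5% loss and between 4 and 5 points at 10%. Under the planned Fisher's exact test the resulting power is 74% and 71%, from a no-loss value of 76%. These figures rest on the protocol's own 10% and 5% rates, on an assumed two-sided 5% level, on equal loss in both arms, and on illustrative loss rates. Removal for side effects can occur only in the experimental arm, so real losses may be unequal.

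This is not something to leave to a separate analysis plan, because A.5 itself fixes the size and describes it as adequate.

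**What to change.** Amend A.5 in two respects:

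1. Say that 424 per group is the number of patients with an observed one-month infection outcome, and that 848 is the number enrolled, if that is what is meant.
2. State alpha and sidedness, the loss the sponsor expects, and the power or detectable difference that 848 enrolled patients then give under Fisher's exact test. At 10% loss, for example, the statement would be about 382 observed per group and 71% power for 10% against 5% at two-sided 5%.

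The expected loss has to come from the sponsor's own follow-up experience, since the protocol contains no basis for it. Using the Fisher calculation also settles the mismatch with the arcsine formula.

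The change takes a few sentences and needs no extra recruitment, procedures or centers. The downside is that a general claim of adequate power becomes an explicit and somewhat less favourable figure.

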The dermatologic surgery staff will be educated on the inclusion criteria for this study. Patients referred to our office with lower extremity lesions will be flagged by the dermatologic surgery staff.

Once flagged, the patient's information will be sent to study personnel who will verify that the patient meets eligibility criteria. A physician will then contact the patient for a pre-operative telephone consultation to discuss participation in the study.

B.6. Informed Consent

At the pre-operative consultation, the study will be described to the subjects by the physician enrolling them. Subjects will be assured that their participation is voluntary and their level of care will not change based on their decision. They will have time to review the consent form and be able to ask any questions prior to signing the consent form.

If the pre-operative consultation is conducted virtually, the investigators will verbally explain the study and provide subjects with a copy of the consent materials electronically (via REDcap or other means) or by mail. Prior to enrollment, attempts will be made to obtain an electronic (if acceptable per institutional policies) or hand-written signature from subjects. However, if the subject is willing to participate but obtaining the signature is logistically burdensome, verbal consent will be accepted and the subject enrolled. A waiver of written documentation of consent [21 CFR §56.109(c)(1) and 45 CFR §46.117(c)(2)] will be requested of the reviewing IRB in order to enroll the subject on the study. The consent form will be reviewed during the pre-operative visit to discuss the research and ensure that the subject is fully informed. Subjects that are mailed a copy of the consent form will be asked to sign and bring it with them on the day of their surgery. Patients that sign the REDcap consent form will be asked to sign a hard copy on the day of their surgery.

C. Study Procedures

C.1. Summary of Methods and Procedures

Patients meeting eligibility criteria will be approached at their pre-operative consultation and asked to participate. After providing informed consent, as previously described, subjects will be randomly placed into one of the two arms.

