Once enrolled, subjects in the experimental group will be prescribed mupirocin 2% ointment and chlorhexidine wash. Instructions for decolonization will be provided to the subjects in a "pre-procedure handout and a medication log in order to help them perform and track the decolonization protocol sufficiently. Subjects in the experimental group will follow decolonization procedures for 5 days prior to surgery.

On the day of their procedure, all subjects will be asked to fill out a demographic survey to evaluate their risk of developing infection. The demographic survey sheet will record the patients' age, sex, prior *Staphylococcus aureus* infections, medications, BMI over 25, smoking status, number of showers per week, and medical history of diabetes, immunosuppression, peripheral vascular disease, and nutritional deficiency. Patients' answers will be recorded in a protected, unidentified database.

Following surgery, all subjects will be asked to send in a picture of their surgical site during the postoperative period at weeks 2 and 4. Patients will submit photos of their surgical site via the Cooper RedCap system. They will receive an email prompting them to upload their photos at these points. Photographs will be evaluated by a study physician upon receipt. After that one month, the patient will be informed that they no longer need to send in any more photos.

Any patient who develops symptoms of an infection or has concerning findings on the pictures will be instructed to schedule a follow up appointment for evaluation. At this visit, their wound will be swabbed for the causative pathogens. The results from the wound culture will be shared with the patients and, if positive for pathogenic bacterial growth, will be started on antibiotics for treatment of their surgical site infection.

Subjects that do not require a follow up appointment will be followed up with a call at one month post-surgery. We will ask these patients if they developed a wound infection or if they had any issues with their surgical site.

C.2. Study Visits

On the day of the procedure, the patient will be given an envelope containing a hard copy of their official consent form to sign (if they did not bring their copy from home) and a demographic survey sheet.

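### Second-intention healing is an inclusion criterion worded as a postoperative state, so applying it as written excludes patients after allocation

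*Protocol*

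**What the plan says.** **Population and criterion.** Protocol B.1 describes patients having Mohs surgery or excision "on the lower extremities that will heal by second intention as determined by the surgeon performing the procedure". B.2 lists as an inclusion criterion "Postoperative wounds healing by second intention".

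**Checks before allocation.** In B.4, once scheduling staff flag a lower-extremity case, "a study physician will review the location and deem if patient an appropriate candidate for the study". B.5 sends the patient's details to "study personnel who will verify that the patient meets eligibility criteria" before the consultation, and C.1 approaches only patients who meet the criteria. None of these sections mentions closure method.

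**Allocation and treatment.** A.4: "The log will alternate between study and control group", and "The patient will be entered into the log in the order that their telehealth was completed, which will determine their study group". C.1: "Subjects in the experimental group will follow decolonization procedures for 5 days prior to surgery". A.2: "The control group will not receive any pre-operative decolonization". The protocol states no masking of the surgeon.

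**Follow-up.** C.1 and C.2 ask every enrolled patient for photographs, and D.6.1 has every enrolled patient contacted at one month. C.7 ends participation only for withdrawal or side effects. No section says what happens to an allocated patient whose wound is not left open.

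**Size.** A.5 asks for 424 per group (848 in total) to detect 10% v 5%, with no stated allowance for such patients.

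**The concern.** An eligibility criterion should be settled before the arm is assigned. Here one criterion can be confirmed only once the wound exists, which is after allocation and after five days of treatment in one arm. The person who determines it is the operating surgeon. With a no-treatment control, an alternating log and no stated masking, that surgeon may know the arm.

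The protocol's own background makes closure type prognostic. Infection was 6.8% in second-intention wounds and 3.2% in sutured wounds (odds ratio 2.22). If patients closed another way are dropped, the arms are compared after a selection that may depend on the arm and is related to the outcome. Proper random allocation would not cure this, because the selection comes later. If they are kept, the comparison also includes wounds outside the stated aim, and the effect may be diluted. The protocol does not choose between these courses.

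**Working it through.** **1. Order of events.** Location review and eligibility check (B.4, B.5) → consultation and consent → log entry, which fixes the arm (A.4) → five days of decolonization or nothing (C.1, A.2) → surgery → wound left open or closed. The B.2 state exists only at the last step, so the B.5 check cannot verify it. At most it could verify an intention, and no passage has an intention recorded.

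**2. The plan's own figure.** Significance level and power are not stated; two-sided 0.05 and 80% are assumed. Arcsine formula: h = 2·asin√0.10 − 2·asin√0.05 = 0.1925; n = 2(1.960 + 0.842)²/h² = 423.7, so 424. The stated figure reproduces. Exact power of Fisher's test (the test named in A.6) at 424 per group, 10% v 5%, is 75.8%. This is the baseline below.

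**3. If patients closed otherwise are dropped.** The share is assumed, because the protocol gives none. n = 424 × (1 − share).

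| Share closed otherwise | n per group | Fisher power, 10% v 5% |
|---|---|---|
| 0% | 424 | 75.8% |
| 20% | 339 | 65.1% |
| 30% | 297 | 58.7% |
| 40% | 254 | 52.0% |
| 50% | 212 | 43.2% |

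**4. If they are kept.** Two further assumptions: the all-site odds ratio of 2.22 applies to the leg, and treatment halves the risk in sutured wounds too. Sutured odds = (0.10/0.90)/2.22 = 0.0501, a risk of 4.77%. Control rate = (1 − share) × 10% + share × 4.77%; treated rate is half of that; 424 per group.

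| Share closed otherwise | Rates | Fisher power |
|---|---|---|
| 20% | 8.95% v 4.48% | 70.1% |
| 30% | 8.43% v 4.21% | 67.1% |
| 50% | 7.38% v 3.69% | 60.4% |

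**5. Selection bias with no true effect.** Two scenarios, with every input assumed.

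- *Mild.* Half the wounds carry 5% risk and half 15%. Both arms leave 60% of low-risk wounds open. One arm leaves 60% of high-risk wounds open, the other 40%. Analysed rates: (0.6×5 + 0.6×15)/1.2 = 10.0% and (0.6×5 + 0.4×15)/1.0 = 9.0%. With 254 and 212 analysed, Fisher's test rejects about 5.3% of the time.
- *Strong.* Each arm loses 20%, at random in control, but those lost from the treated arm carry twice the 10% average risk. Treated rate: (0.10 − 0.20×0.20)/0.80 = 7.5% against 10%. With 339 per arm, the normal approximation gives a type I error of about 21%.

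The result runs from negligible to serious depending on inputs the documents do not supply.

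**The case against.** The best objection is that B.1 looks forward and does not say when the surgeon decides. B.5 and C.1 place eligibility before the consultation, so a judgement of intended closure before allocation is compatible with the text. This stands against any claim that closure is settled only at surgery. It does not rescue the wording of B.2, which names the postoperative wound.

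Second, a reader might infer that the surgeon decides who stays in the trial. The documents do not support that: photographs and calls cover everyone enrolled, and no passage removes a patient for closure type. The analysis set may be defined in a statistical analysis plan that is not shown. What remains is that failing an inclusion criterion is an ordinary ground for exclusion, and nothing in the protocol rules it out. An analysis plan could limit the harm but could not move the criterion ahead of allocation.

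Third, a reader might take the surgeon to be openly unmasked. That is a reasonable inference from an untreated control, an alternating log and silence on masking, but the protocol never says that the surgeon is told the arm.

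Fourth, the bias may be small or may work against the intervention. If surgeons were less willing to leave an undecolonized high-risk wound open, the control arm would lose high-risk wounds and its rate would look better. This also stands: neither size nor direction is established.

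**Conclusion.** The point holds as a defect in how and when eligibility is fixed. B.2 as written can be confirmed only after allocation and treatment, it is judged by someone who may know the arm, and it turns on a factor the protocol associates with infection. No section requires intended closure to be recorded first, and none says how patients closed otherwise are handled.

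It does not follow that the trial is shown to be biased, that patients are in fact removed, or that 424 per group is miscalculated; that figure reproduces under conventional assumptions. The power ranges (65–43% if dropped, 70–60% if kept, against 76%) rest on an assumed 20–50% share closed otherwise and an assumed two-sided 0.05 level. The second range also rests on the all-site odds ratio holding on the leg and on treatment halving the risk in sutured wounds. They are illustrations, not estimates. Severity: should-fix, with moderate confidence.

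**What to change.** 1. **Reword the B.2 criterion** to: *second-intention healing planned by the operating surgeon, recorded before the patient is entered in the allocation log*. This makes it a fact fixed before allocation and leaves the closure choice at surgery unrestricted.
2. **State the comparison.** The primary comparison is all patients so enrolled, in their allocated arm whatever the actual closure. Report the number closed otherwise by arm, and give the subset actually left to heal by second intention as supporting only. The analysis detail can sit in the statistical analysis plan, provided the protocol says that these patients are kept.

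The cost is a protocol amendment, one extra log field and some dilution of the effect from wounds closed otherwise. The question becomes the effect in patients for whom second-intention healing is planned, which is also the information available when decolonization has to start. The 848 contains no allowance for that dilution, and the documents give no share from which to set one.

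Where existing staffing allows, the operating surgeon should not be told the arm before the closure choice is recorded. This is desirable but not a required part of the fix, since the documents do not show that it is feasible at all 10 centres.
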